	
Participants with a reported history of a previous malignant neoplasm, a known hypersensitivity to β-TCP or rhPDGF-BB, a Titanium metal allergy, or any other health condition or medication regimen that, in the opinion of the investigators, may adversely affect bone healing will be excluded.
 
Women who are pregnant or nursing at the time of recruiting will be excluded.

Outcomes	
Radiographic image analysis of osseous architecture changes at study sites over time
 
Soft-Tissue aesthetic assessments
 
Patient Satisfaction assessments
 
Data analysis – results and conclusions
 
Final report

Statistical Analyses	
The general approach to statistical analysis of the study aims will be based on mixed-model analysis of variance (ANOVA). This approach will accommodate the inclusion of correlated observations due to study subjects potentially contributing measurements of more than one single tooth site to the analysis.
 
The sample distributions will be examined for each outcome variable. If these distributions depart substantially from normality, transformations of the data will be evaluated. If normality cannot be established by transformation, rank-based analyses will be used.
 
Subjects will be included as a random effect on the analyses that include multiple observations per subject. For analysis of histological data, only one tooth site per subject will be evaluated and the model will not include a random effect.
 
Smoking status will be included in all models so that the analysis will correspond to the study's randomization strategy.
 
For the aims in which interaction terms are of interest, significant interaction terms will be investigated using plots of least-square means and separate post-hoc analyses for individual time points.

Table of Contents

Section	Title	Page
1:	Background and Significance	6
2:	Investigational Design	9
3:	Study Population	10
4:	Study Procedures	11
5:	Tissue Biopsy & Surgical Implant Placement	15
6:	Restoration of Implants	17
7:	Longitudinal Follow-up Protocol	17
8:	Radiographic & Photographic Surveys	18
9:	Adverse Event Reporting	19
10:	Criteria for Success	19
11:	Costs to Participants	20
12:	Outcomes and Analyses	21
13:	Confidentiality	25
14:	Regulatory Issues	26
15:	Ethical Issues	27
16:	Literature Cited	28
17	Study Personnel	31
18	Signature Page	32

Appendices

A:	FDA 510(k) Device Approval
B	Safety and Effectiveness – GEM-21S™
C:	Informed Consent

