3.0 STUDY POPULATION

3.1 Entrance Criteria

Eighty healthy adult patients (20 in each group) of any ethnicity or gender whose treatment plan includes extraction of maxillary anterior teeth and/or mandibular and/or maxillary pre-molars and their replacement with root-form dental implants will be consecutively recruited for enrollment in the study.

The study will include an initial minimum of six time-sensitive, clinic visits over eight consecutive weeks. Implants will be placed 8 weeks after extractions. Following implant placement, additional visits, necessary for health maintenance and implant restoration, will be scheduled at the study dentist's discretion. Participants will return for two follow-up visits at 12 and 24 months after implant placement.

Only treatment of non-adjacent sites will be included in the database. Each participant may have up to four non-adjacent sites selected for inclusion as study treatment sites.

Participants must be at least 19 years old with demonstrated ability to understand the proposed treatment recommendations and prognosis and be able to provide informed consent, in English, without the aid of ad-hoc translation from another language. Decisionally-impaired adults and/or minors, who cannot consent for themselves, will not be enrolled; women who are pregnant or lactating at the time of enrollment will be excluded. Women will be tested for current pregnancy status.

Prior to enrollment, prospective participants must agree to be available for the entire duration of the study, be compliant with needed study-related evaluations and demonstrate a willingness to comply with strict time-line requirements. Certain health and medication exclusions apply (table 1).

Table 1 Entrance Criteria

Inclusion	Exclusion
Existence of one or more non-adjacent teeth in the aesthetic zone that are scheduled for extraction	Pregnancy or nursing at the time of enrollment
Healthy enough to undergo the proposed therapy without compromise to their existing health status	Previous malignant neoplasm
Demonstrated willingness to comply fully with protocol time-line and procedural requirements	A known hypersensitivity to β -TCP or rhPDGF-BB
At least nineteen years old	A known hypersensitivity to Titanium metal
Able to read and understand written English without the aid of ad hoc interpretation	Any health condition that in the opinion of the clinical investigators may adversely affect bone healing

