8.0 RADIOGRAPHIC AND PHOTOGRAPHIC SURVEYS

8.1 Cone Beam Computed Tomography

Cone beam computed tomography (CBCT) images will be used to obtain a 3-dimensional database of the patient's anatomy from the volumetric tomography. Axial, sagittal, and cross-images will be reconstructed to measure the tooth socket volume. Hounsfield units will be calculated to assess the relative tissue density for each study site. CBCT scans will be obtained after the completion of the extraction and grafting procedures and again at 8 weeks after the extractions.

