12.4 Statistical Analysis

The general approach to statistical analysis of the study aims will be based on mixed-model analysis of variance (ANOVA). This approach will accommodate the inclusion of correlated observations due to study subjects potentially contributing measurements of more than one single tooth site to the analysis.

The sample distributions will be examined for each outcome variable. If these distributions depart substantially from normality, transformations of the data will be evaluated. If normality cannot be established by transformation, rank-based analyses will be used.

Subjects will be included as a random effect on the analyses that include multiple observations per subject. For analysis of histological data, only one tooth site per subject will be evaluated and the model will not include a random effect.

Smoking status will be included in all models in order to account for differences in response between smokers and non-smokers, and so that the analysis will correspond to the study's randomization strategy. Comparisons between smokers and non-smokers are not a primary interest in the study.

For aims in which interaction terms are of interest, significant interaction terms will be investigated using plots of least square means and separate post-hoc analyses for individual time points.

Hypothesis 1

Differences among the four groups will be evaluated by the overall F-test for the ANOVA. Pairwise comparisons among group means will be conducted using Tukey's test. Contrasts will be constructed to address each specific aim (SA).

SA-1: Compare alveolar ridge dimensions in grafted extraction sockets to that of sites healed without grafts after 8 weeks of post-extraction healing.

This SA will be addressed by comparing the combined mean of the three graft groups (FDBA/TCP, DDBA/TCP/PRP, FDBA/TCP/PDGF) with that of the CONTROL group by calculating a contrast and the corresponding F-test. Pairwise comparisons among means will be conducted using Tukey's test..

Hypothesis II

The addition of growth factors to bone grafting materials will enhance osseous and soft tissue healing.

SA-2: Assess the efficacy of bone grafting with and without enrichment with growth factors to preserve the volume of bone in extraction sockets.

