This SA will be addressed using mixed-model ANOVA to compare mean bone volume among the four groups. Post-hoc pairwise comparisons will use Tukey's test. The effect of growth factors enrichment will be addressed using contrasts and F-tests to compare the mean of Group-4 with those of each of the other groups. If there is not a significant difference among the group means of Groups 1-3, the combined mean of these three groups will be compared with that of Group-4.

SA-3: Compare soft tissue healing between groups at week-1, week-2, week-4 and after 8 weeks of healing.

The analysis of SA-3 will be mixed-model ANOVA including measurements of healing made at each time points. Time will be included in the model in order to account for unequal spacing of the observational times. The statistical test that will be of primary interest will be the F-test for Group by time interaction.

SA-4: Assess quantitative bone fill across groups after 8 weeks post-extraction healing.

Qualitative bone fill will be compared among four groups using mixed-model ANOVA and the 8 week measurement only. Post-hoc pairwise comparisons will use Tukey's test.

SA-5: Compare qualitative bone fill across groups after 8 weeks post-extraction healing.

Percent new bone, percent residual graft, and percent soft-tissue will be compared among the four groups using ANOVA. For this analysis, there will be a single measurement of each of the variables per participant, so correlated observations will not be an issue in the analysis. Post-hoc pairwise comparisons will use Tukey's test.

SA-6: Assess the relationship of osseous healing and implant stability at insertion across groups after 8 weeks post-extraction healing.

This SA will be addressed by including the implant stability measure as a predictor variable in the analysis of osseous healing. The statistical test that will be of primary interest for this analysis will be the two-factor interaction of stability and group.

Hypothesis III

Laser thread-textured (LTT) dental implant will preserve longitudinal peri-implant crestal bone more effectively than implants with Resorbable blast texturing (RBT).

SA-7: Assess the efficacy of LTT and RBT surface topographies when surgically implanted into extraction sockets.

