A conservative approach to power estimation was used, assuming an effective sample size of 25 observations per extraction-implant group. Power calculations utilized the Power and Precision, release 2.00, (Borenstein, 2000) and nQuery Advisor 6.0 (Janet D. Elashoff, 1995-2005) software packages. Power to detect a “medium” effect size, corresponding to a difference between group means equal to 0.50 times the within-group standard deviation (sd) was calculated. Also, the effect size detectable with 80% power was calculated. All power estimates were based on two-sided testing at the 95% confidence level.

The power for SA-1 is largely determined by the size of control group, since the primary comparison is equivalent to a t-test of the mean of the controls vs others. Thus, the assumed effective sample sizes of 25 and 75 would yield approximatey 57% power to detect a medium effect size. The difference detectable with 80% power would be approximately 0.65sd .

Power for SA-2, SA-4 and SA-5 was based on a one-way ANOVA model. The proposed sample size would provide 52% power to detect a medium effect size or 80% power to detect an effect size equivalent to a two-group difference of 0.34sd . These approximations also apply to SA-3, with the appropriate sd being the within-group standard deviation of the changes across the observation times.

The total sample size for SA-5 would be 80, or 20 per group, since this SA is based on histology, with a single extraction per participant. Power to detect a medium effect size would be 42%. The effect size detectable with 80% power is equivalent to a two-group difference of 0.72sd.

Power for SA-6 was based on linear regression with a four-category dummy variable. If stability and group each explain 10% of the observed variance, the proposed sample size would provide 80% power to detect an increment of 8.6% in explained variance for the stability*group interaction.

Power for comparison of rates of infection signs for SA-7 was based on the chi-square test for the odds ratio. The proportions in the two groups were centered on 0.50, in order to provide a conservative estimate of power. The effective sample size of 50 per group would provide 80% power to detect an odds ratio of approximately 3.2 for the association between implant type and infection.

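### SA-2 and SA-4 make no use of starting socket size, which is recorded at every site; adjusting for a measure that grafting does not alter would add precision at little cost

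*Combined protocol and SAP*

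**What the plan says.** The aim of SA-2 is to "Assess the efficacy of bone grafting with and without enrichment with growth factors to preserve the volume of bone in extraction sockets". Its analysis in section 12.4 reads: "This SA will be addressed using mixed-model ANOVA to compare mean bone volume among the four groups". It names no week, change score or baseline covariate. SA-4, on bone fill, is analysed "using mixed-model ANOVA and the 8 week measurement only". The only covariate that section 12.4 names for all models is smoking status, with a subject random effect where a participant has several sites.

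The Outcomes row of the synopsis lists "Radiographic image analysis of osseous architecture changes at study sites over time". Section 8.1 says that "CBCT scans will be obtained after the completion of the extraction and grafting procedures and again at 8 weeks after the extractions", with the images reconstructed to measure socket volume. No analysis in section 12.4 mentions the first of these scans.

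Starting socket size is also recorded directly. Section 4.6 has the socket walls assessed and measured in all groups, and item 4.8-1 specifies their mesio-distal and bucco-lingual distances. No model uses these either.

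Section 12.5 bases power for SA-2 and SA-4 on a one-way ANOVA without a covariate. It brings in the standard deviation of changes only for SA-3, SA-8 and SA-9.

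**The concern.** An aim about preservation refers to a starting state, and the trial measures that state at every site, yet the two CBCT aims do not use it. Eligible sites run from maxillary anterior teeth to premolars of both jaws, and randomisation is stratified by smoking only. Socket size plausibly varies with tooth type. If 8-week volume varies with socket size, that variation inflates the residual variance, and chance differences between arms of 20 participants add noise to the group means.

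What is at stake is the precision of two of the five aims under Hypothesis II. By the plan's own figure they have little more than an even chance of detecting a medium effect.

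**Working it through.** **Inputs from the documents**
- Participants: "Eighty healthy adult patients (20 in each group"), four groups.
- Section 12.5: power was computed "assuming an effective sample size of 25 observations per extraction-implant group". The stated 52% reproduces with 25 per extraction group, 100 in total.
- Section 12.5: "All power estimates were based on two-sided testing at the 95% confidence level", so alpha is 0.05.
- Section 12.5: a medium effect is 0.50 sd. In the one-way ANOVA this is Cohen's f = 0.25.

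**Input assumed**
- r, the within-group correlation between initial socket size and the 8-week outcome. The documents give no value, so a range of 0.1 to 0.7 is shown. With two distances in the model, r is the multiple correlation.

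**Step 1: reproduce the plan's figure.** The noncentrality is λ = N f² = 100 × 0.25² = 6.25. The F-test has 3 and 96 df, with a critical value of 2.70. Power is 51.8%, against the stated 52%. The plan's power therefore takes no credit for any baseline measure.

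**Step 2: add a covariate.** Residual variance is multiplied by (1 − r²), so λ = 6.25 / (1 − r²), with 3 and 95 df. The equivalent N is 100 / (1 − r²). The last column is the two-group difference (2f) detectable with 80% power, which is 0.674 × √(1 − r²) sd.

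| r | λ | Power | Equivalent N | Detectable difference |
|---|---|---|---|---|
| none | 6.25 | 51.8% | 100 | 0.67 sd |
| 0.1 | 6.31 | 52.2% | 101 | 0.67 sd |
| 0.3 | 6.87 | 56.1% | 110 | 0.64 sd |
| 0.5 | 8.33 | 65.4% | 133 | 0.58 sd |
| 0.7 | 12.25 | 83.2% | 196 | 0.48 sd |

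Losing two degrees of freedom instead of one leaves the rounded powers at 52%, 56%, 65% and 83%. The plan prints 0.34 sd as the 80% detectable difference for these aims. That figure equals f = 0.337, which as a two-group difference is 2 × 0.337 = 0.67 sd, the value used here.

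**Step 3: why the first CBCT is not a safe default.** Section 4.7 packs groups 2 to 4 to complete fill and leaves group 1 ungrafted, and the scan follows. Suppose grafting moves the first-scan reading by s sd. Adjusting for it then shifts the graft-versus-control estimate by −r × s, and subtracting it shifts the estimate by −s.
- s = 0.3, r = 0.7: the shift is −0.21 sd, and 0.21 / 0.50 = 42% of the medium effect.
- s = 1, r = 0.5: a true 0.50 sd becomes 0.50 − 0.50 = 0 with adjustment, and 0.50 − 1 = −0.50 sd with subtraction.

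**Step 4: why a change score is not the answer.** Its variance factor is 2(1 − r). Even with an untouched baseline, power is 38% at r = 0.3, 52% at r = 0.5 and 76% at r = 0.7. Below r = 0.5 it does worse than the unadjusted analysis.

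**The case against.** The strongest defence is that analysing SA-4 at week 8 alone is coherent. The aim is fill after eight weeks of healing, and fill on the first scan is set by the assigned treatment. That stands, and it is why first-scan fill should not enter the model. It does not count against a socket-size measure that is free of the graft.

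A reader might infer that SA-2 is explicitly confined to one 8-week reading. It is not: SA-2 names no time point. The single reading is a fair inference from the missing time term and the one-way ANOVA power basis, but what the text shows is an omission to be filled.

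A reader might also infer that the comparison is invalid because preserved volume cannot be told from a socket that began larger. Randomisation answers this. Socket size is balanced in expectation, and chance imbalance is already reflected in the standard error.

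A third tempting reading is that the first CBCT offers precision already paid for. The documents do not say that the bony wall can be told from packed graft on that scan. Item 4.8-2 also expects dehiscence and fenestration defects, where a traced boundary needs a further rule.

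Finally, the synopsis outcome worded as change over time does not name CBCT and could equally describe the later crestal bone radiographs. It is weak evidence that SA-2 or SA-4 was meant as a change analysis.

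**Conclusion.** The point holds as a cheap gain in precision, not as a flaw in validity. SA-4 is restricted to week 8, SA-2 leaves its time point unstated, and neither uses a starting socket size that the trial records in all groups.

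The gain depends on r. Power is essentially unchanged at r = 0.1, rises by about 4 points at 0.3 and 14 at 0.5, and by about 31 points at 0.7. These figures assume a covariate that grafting does not alter and 25 effective independent sites per group. They also assume that adjustment reduces variance in the same proportion between and within participants. The gain for SA-4 would be smaller if fill is expressed as a percentage of the socket, which the plan does not say.

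**What to change.** 1. State in SA-2 that the outcome is the 8-week CBCT bone volume.
2. Add to the SA-2 and SA-4 models a site-level covariate for initial socket size, keeping smoking status and the subject random effect. The default is the mesio-distal and bucco-lingual socket-wall distances of item 4.8-1. State that they are taken before any graft is placed; section 4.6 lists them before grafting but does not say so outright. Do not use the soft-tissue wound distances of item 4.8-3, which are taken after suturing.
3. Use a wall-traced socket volume from the first CBCT only if a single tracing rule is shown to give comparable readings in filled and unfilled sockets. The rule should be applied blind to arm where possible and should cover dehiscence and fenestration sites.
4. Do not adjust for or subtract fill on the first CBCT. Keep any change from that scan descriptive.
5. Reconcile the synopsis (Procedures), which places the first scan directly after extraction, with sections 4.7 and 8.1, which place it after grafting.
6. State whether SA-4 fill is an absolute volume or a percentage of the socket.

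The cost is SAP wording and one or two model degrees of freedom. The default covariates need no new measurement.

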Data from these studies support the potential of different bone grafting materials to preserve the alveolar ridge after extraction. Concomitant investigations, however have reported that grafting materials may, in fact, impede natural post-extraction healing⁷. Thus the most efficacious intervention remains clouded by uncertainty.

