4.7 Grafting Extraction Sockets

After extractions, sockets will be grafted according to each participant's assigned randomization group.

Group-1: Each socket will be irrigated with sterile saline and allowed to heal naturally [control group].

Group-2: Each socket will be grafted with freeze dried bone allograft (FDBA) mixed with Tri-calcium phosphate (TCP) 8:2 ratio; reconstituted with sterile saline.

4.7-2a Irrigate sockets with sterile saline

4.7-2b Pack the graft into each of the study sites using mild pressure achieving complete fill of the sockets.

4.7-2c Trim a 3mm section of collaplug and secure it over the grafted areas with 4.0 Vicryl crossing mattress sutures.

Group 3: Each socket will be grafted with an 8:2 ratio FDBA/TCP graft reconstituted with Platelet Rich Plasma (PRP).

4.7-3a Collect 9-18cc blood sample from the patient via venipuncture prepare the PRP following the Cascade Fibrinet System (Appendix A)

4.7-3b Mix PRP in the FDBA.TCP graft.

4.7-3c Irrigate sockets with sterile saline.

4.7-3d Pack the graft into each of the study sites using mild pressure achieving complete fill of the sockets

4.7-3e Trim a 3mm section of collaplug and secured it over the grafted areas with 4.0 Vicryl crossing mattress sutures.

4.7-3f Once secured in place, the soak the collaplug with PRP.

Group 4: Each socket will be grafted with an 8:2 ratio FDBA/TCP graft reconstituted with recombinant platelet derived growth factor (PDGF).

4.7-4a Irrigate sockets with sterile saline.

4.7-4b Apply PDGF into the sockets completely wetting all socket walls.

4.7-4c Mix PDGF with GEM-21S (product insert Appendix B)

4.7-4d Pack the graft into each of the study sites using mild pressure achieving complete fill of the sockets

4.7-4e Trim a 3mm section of collaplug and secure it over the grafted areas with 4.0 Vicryl crossing mattress sutures.

4.7-4f Once secured in place, soak the collaplug with PDGF.

After completion of procedures the Essix retainer (if used) will be fitted and placed.

A CBCT scan will be made to include images of each study site. Prescriptions for anti-bacterial mouth wash, antibiotics, and pain relief will be provided based on individual patient needs. An ice-pack will be dispensed. Verbal and written home care instructions will be given and the patient will be scheduled for a follow-up appointment.

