10.0 CRITERIA FOR SUCCESS

10.1 Grafts

The success criteria for this investigation are determined as follows: Grafts will be deemed successful if there are no reported symptoms or clinical signs or of post-application allergy, toxic reactions or evidence of gross local or systemic infections.

Histological and histomorphometric analyses will provide evidence of the relative success or failure of graft materials to enhance formation of new osseous tissue in extraction sockets. Results will be compared across experimental groups and between experimental groups and controls.

A site that fails to meet the stated criteria for success, or where the width of the ridge remains too narrow for implant insertion will be re-grafted (an offer that patients may decline). The site may receive an implant at a later date but the site will be exited from the study results.

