12.1 Objective Data

Bone biopsies preserved in the trephines and stored in formalin will be submitted to UAB's CMBD (Name of facility) Core Laboratory. Trephine core 2x6mm will be stained with hematoxylin and eosin and processed for histologic and histomorphometric analysis. Amount of bone fill and remaining bone graft (% of new bone fill, % of residual graft and % of soft tissue) material will be determined and compared across groups.

Cone Beam Computed Technology (CBCT) will be used to capture quantitative natural bone fill and bone fill following grafting applications at each extraction site.

Image analysis software will be used to capture images from the standardized radiographs taken at 12 and 24 months following implant placement. Analysis procedures will assess the implant/bone interface and measure changes in adjacent crestal alveolar bone levels over time.

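### SA-5: percent new bone, if taken over the whole core, cannot on its own separate space occupied by residual graft from impeded bone formation when grafted sites are compared with ungrafted controls

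*Combined protocol and SAP*

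**What the plan says.** Section 12.1 (Objective Data) describes the specimen: "Trephine core 2x6mm will be stained with hematoxylin and eosin and processed for histologic and histomorphometric analysis". Each core is reported as three shares, "of new bone fill, % of residual graft and % of soft tissue". Section 12.4 defines the aim, "SA-5: Compare qualitative bone fill across groups after 8 weeks post-extraction healing", and its test: "Percent new bone, percent residual graft, and percent soft-tissue will be compared among the four groups using ANOVA", with Tukey's test for pairwise comparisons. There is one core per participant, so no random effect is needed.

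The groups differ in what can be in the core. In section 4.7, Group 1: "Each socket will be irrigated with sterile saline and allowed to heal naturally [control group". For each of Groups 2-4 the instruction is: "Pack the graft into each of the study sites using mild pressure achieving complete fill of the sockets".

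Section 10.1 says how the histology will be read, and states that grafted groups will be compared with controls: "Histological and histomorphometric analyses will provide evidence of the relative success or failure of graft materials to enhance formation of new osseous tissue". Section 1.1 raises the opposite possibility, that "grafting materials may, in fact, impede natural post-extraction healing".

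The sections supplied give no denominator for the percentages, no graft-free measure, and no guidance on reading percent new bone against a group that has no graft.

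**The concern.** In a control core, everything is bone or soft tissue. In a grafted core, some of the area may still be graft particles at 8 weeks. Two sockets in which the same fraction of the non-graft tissue has become bone can therefore show different percentages of new bone, and the grafted one shows less.

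That difference has the same sign as the effect section 1.1 worries about, and section 10.1 makes histomorphometry the evidence on graft success or failure. A lower percentage in Groups 2-4 could be reported as grafting impeding bone formation when it reflects only where the particles sit. A true benefit of grafting could be masked in the same way.

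**Working it through.** **Inputs from the documents.** Four groups of 20, one core each (section 12.5, SA-5). Two-sided 5% level (section 12.5). Four-group ANOVA, then Tukey (section 12.4). Residual graft in Group 1 is zero by design (section 4.7).

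**Inputs not in the documents (assumed, with ranges).** Bone share of the non-graft tissue, b: 30-50%. Residual graft share of the core at 8 weeks, g: 5-30%. Between-participant sd: 10-20 points. Equal sd in all groups; smoking term ignored.

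**Step 1. The plan's own figure.** Section 12.5 gives 42% power for a medium effect in SA-5. With Cohen's f = 0.25 and N = 80, the noncentrality is 80 x 0.25² = 5.0 on 3 and 76 degrees of freedom, and power is 42.0%. The figure reproduces, so the same method is used below.

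**Step 2. The gap under equal healing of the non-graft tissue.** Controls show b. Grafted sites show b(1 - g). The gap is b x g.

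- b = 40%, g = 20%: 40 against 32, a gap of 8 points.
- b = 50%, g = 20%: 50 against 40, a gap of 10 points.
- Whole assumed range: 30 x 0.05 = 1.5 points to 50 x 0.30 = 15 points.

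**Step 3. How often the planned tests would flag it.** With one control mean higher by d sd units and three equal graft means, f² = d² x (1/4)(3/4) = 0.1875d², so the noncentrality is 80 x 0.1875d² = 15d². At sd 15:

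| b | g | Gap (points) | d | 15d² | ANOVA significant |
|---|---|---|---|---|---|
| 40% | 5% | 2 | 0.13 | 0.27 | about 6% |
| 40% | 10% | 4 | 0.27 | 1.07 | 12% |
| 40% | 20% | 8 | 0.53 | 4.27 | 36% |
| 50% | 20% | 10 | 0.67 | 6.67 | 54% |
| 40% | 30% | 12 | 0.80 | 9.60 | 72% |

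By simulation, Tukey's test places at least one graft group significantly below control in about 36% of trials for the 8-point gap and 54% for the 10-point gap. For any one given graft-control pair the figures are about 18% and 31%. Over the whole assumed range the ANOVA figure runs from about 5% (no more than the nominal level) to about 100%.

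For scale, the plan's medium difference of 0.5 sd is 7.5 points at sd 15. With b = 40% it is reached at g = 7.5/40, about 19% residual graft.

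**Step 4. What a graft-free share does.** The ratio is new bone / (new bone + soft tissue). Take b = 40%, g = 20%.

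| What the graft displaces | Whole-core % new bone, control v grafted | Ratio, control v grafted |
|---|---|---|
| Bone and soft tissue in proportion | 40 v 32 | 40 v 32/80 = 40 |
| Soft tissue only | 40 v 40 | 40 v 40/80 = 50 |

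In the first case the whole-core measure shows a deficit and the ratio shows none. In the second the ratio shows a gain and the whole-core measure shows none. The two measures bracket these cases.

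**The case against.** **Whole-core percent is a legitimate estimand.** If particles take up space and the socket holds less new bone, that is a real difference in socket content, and randomisation estimates it without bias. This stands. A reader might infer that the outcome is biased against grafting, or that the deficit follows from arithmetic alone. The documents do not support that: the gap needs graft to displace would-be bone as well as soft tissue. The ceiling of 100 minus residual graft does not create it; at 20% graft the ceiling is 80%, well above 40%. What remains is narrower: whole-core percent does not by itself answer whether grafting impedes healing.

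**Substituting the ratio would be no better.** This also stands. Step 4 shows it favours grafting by 10 points when only soft tissue is displaced, so it belongs beside the whole-core measure and not in its place.

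**A contrast of control with all grafts gives larger figures.** With 20 against 60 participants it would be significant in 53-72% of trials for the 8-10 point gaps. SA-5 does not name that contrast. Section 12.4 says contrasts will address each aim, but says so under Hypothesis 1, and spells out the graft-control contrast for SA-1. The ANOVA and Tukey figures are the ones that apply.

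**Residual graft is reported too, so dilution would be visible.** True, but the plan gives no rule for using it when interpreting new bone. The three shares sum to 100, which makes their tests dependent but not wrong; dropping one would change no result.

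**SA-5 sits under the growth-factor hypothesis.** Graft against no graft is tested on ridge dimensions in SA-1, which limits the weight of this point. However, section 10.1 explicitly uses histology for the control comparison.

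**Conclusion.** The point holds as a limit on what SA-5 can conclude, not as a demonstrated bias. In comparisons with Group 1, percent new bone of the whole core mixes displacement by graft with any effect on bone formation. The 8-10 point gap, flagged in about 36-54% of trials, rests on assumed values for bone share, residual graft and sd, and on graft displacing bone and soft tissue alike. With 5-10% residual graft the effect is small. Section 1.1 cites a different graft mineral still present at 9 months, which makes residue at 8 weeks plausible but does not give its amount here.

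The whole-core denominator is an inference from the three-part split. The Manual of Procedures is listed as an appendix but is not in the text reviewed, and may define it.

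A reader might extend the point to the growth-factor comparisons. Groups 2-4 all receive an 8:2 FDBA/TCP graft (section 4.7), so those comparisons are less exposed and can stay as planned.

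**What to change.** In section 12.4, SA-5:

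1. State the denominator of each percentage, and confirm it against the histomorphometry procedure.
2. Keep percent new bone of the whole core as the description of what the socket contains, analysed as planned.
3. For comparisons with Group 1, add new bone / (new bone + soft tissue), analysed by the same ANOVA and Tukey procedure.
4. Conclude that grafting impedes or enhances new bone formation only where both measures differ from Group 1 in the same direction. Where they disagree, report that displacement and healing cannot be separated.

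The cost is a few lines of SAP text and one more reported measure, calculated from readings already planned; no extra tissue, visits or participants. The price in inference is a more cautious conclusion when the two measures disagree: requiring both can be no more powerful than the weaker one alone, in an aim whose stated power for a medium effect is already 42%.
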